### **Conditions for interruption of dosing to individuals.**

If there is evidence of hypersensitivity (i.e. wheal as well as flare), subjects can have paracetamol and antihistamines and continue in the trial as per the study schedule.

Injections and treatment will be immediately discontinued (but follow up will continue) in any subject who:

1. Experiences a worsening local wheal or flare reaction at the injection site exceeding 5 cm.
2. Experiences a serious adverse reaction or an allergic event suggestive of systemic hypersensitivity requiring more than local therapy (e.g. requiring steroids, bronchodilators, or adrenaline).
3. Becomes pregnant (see section 8 withdrawal/exit criteria).

**Conditions for suspending further dosing to all subjects.** If any individual in the study experiences a SUSAR further dosing of all subjects at all sites will be suspended pending review by the Data Safety Monitoring Board and discussion with the CI and Sponsor. Advice will be sought from the DSMB regarding re-starting the study.

A substantial amendment application will be submitted to the Regulatory Agencies to resume the trial.

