**All serious adverse events will be shared within 24 hours with the other recruiting site.**

**Sentinel dosing.** The first patient dosed with GNP-peptide will be observed for 6 hours post dose. Temperature, blood pressure and heart rate will be recorded at the following intervals post injection: 15 mins, 30 mins, 45 mins, 1 hour, 1 hour 30mins, 2 hours, 2 hours 30 mins, 3 hours, 4 hours, 5 hours and 6 hours. The injection site will be observed at the following intervals post injection: 5mins, 10 mins, 15 mins, 30 mins, 45 mins and 1 hour. A follow-up phone call will be made to the subject 24 hours after the first dose. No additional patients will be able to be recruited until this 24 hour period is completed (“lock-out period”).

If no serious adverse events are observed, subsequent subjects will also be observed for 6 hours after their first injection. If no serious adverse events are observed, then subjects will be observed for a minimum of 1 hour post dose, or 2 hours if there are any symptoms of signs of hypersensitivity. This time period has been chosen as the only anticipated severe reactions is one of hypersensitivity which, if systemic, would be apparent within 60 mins of intradermal dosing. See section 10.2 for further discussion of hypersensitivity.

Each subject will be contacted by telephone 24 hours after each dose.

The trial manager will communicate with clinical staff by email and telephone to keep both sites up to date with screening and recruitment activity. Weekly teleconferences between sites will take place during the screening and recruitment phase and the trial manager will inform clinical staff at both sites when the first patient is going to be dosed and report to them afterwards regarding whether any AE's were experienced. This will negate the possibility of two subjects starting treatment on the same day. Close communication between sites will be maintained throughout the trial and details of any adverse reactions will be communicated to the other trial treatment site by email, in addition to the standard pharmacovigilance procedures.

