## 10.2 Hypersensitivity

Induction of hypersensitivity to C19-A3 GNP will be assessed by a period of observation of subjects and during the immediate period after peptide injection. Local hypersensitivity may manifest as an increasing wheal and flare reaction at the site of peptide injection. The first patient dosed with GNP-peptide will be observed for 6 hours post dose – see section 7.3. Any adverse reactions will be communicated to the other trial treatment site by email, in addition to the standard pharmacovigilance procedures. Subsequent subjects will also be observed for 6 hours. If no serious adverse events are observed post first dose, subsequent visits will have an observation period of a minimum of 1 hour post dose, or 2 hours if there are any symptoms of signs of hypersensitivity. This time period has been chosen as the only anticipated severe reactions is one of hypersensitivity which, if systemic, would be apparent within 60 mins of intradermal dosing.

Observation will be by inspection of the injection site at 5 minute intervals for the first 15 minutes and then 15 minute intervals for a further 45 minutes. If any reaction is present and not resolving over this period, observation will be extended to 15 minute intervals until the reaction is reducing and < 1cm in diameter. Maximum size of any redness or swelling at the injection site will be recorded at each visit at which study drug is given (visits 1-3). Systemic hypersensitivity may manifest as shortness of breath; skin rash; tissue swelling; collapse. Subjects will be inspected for such signs at 5-minute intervals for the first 15 minutes and then at 15 minute intervals for a further 45 minutes. Pulse and blood pressure will be recorded at 15 minute intervals over this time. Any adverse events during this observation period will be recorded. To minimise any risk that might result from hypersensitivity:

- IMP administration should ONLY performed in a clinical research environment appropriate for phase 1 studies in which resuscitation facilities are immediately available.
- Facilities for treatment of a major hypersensitivity reaction, adrenaline, oxygen, intravenous infusion, head-down position, blood pressure and pulse monitoring should be available in the immediate environment of the subject, with access to hydrocortisone and antihistamines.
- Subjects should not be treated by a lone-worker unless he/she has immediate access to clinically trained support.

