### **11.1 Definitions**

An Adverse Event (AE) is any untoward medical occurrence in a participant to whom an investigational medicinal product (IMP) has been administered, including occurrences which are not necessarily caused by or related to that product.

An Adverse Reaction (AR) is any untoward and unintended response, in a participant, to an IMP which is related to any dose administered to that participant. An Adverse Reaction is an Adverse Event with a causal relationship to the IMP.

Serious Adverse Event (SAE), Serious Adverse Reaction (SAR) or Serious Unexpected Suspected Adverse Reaction (SUSAR) is defined as an Adverse Event, Adverse Reaction or unexpected Adverse Reaction that:

- results in death;
- is life-threatening;  
The term “life-threatening” in the definition of serious refers to an event in which the participant was at risk of death at the time of the event; it does not refer to an event which hypothetically might have caused death if it were more severe;
- Requires hospitalisation or prolongation of existing hospitalisation. Hospitalization is defined as an inpatient admission, regardless of the length of stay, even if the hospitalization is a precautionary measure, for continued observation. Pre-planned hospitalisation e.g. for pre-existing conditions which have not worsened or elective procedures does not constitute an adverse event;
- results in persistent or significant disability or incapacity;
- consists of a congenital anomaly or birth defect; or
- is medically significant;  
Other events that may not result in death are not life-threatening, or do not require hospitalisation may be considered as a serious adverse event when, based upon appropriate medical judgement, the event may jeopardise the participant and may require medical or surgical intervention to prevent one of the outcomes listed above.

Pregnancy in either a participant or the partner of a participant taking trial medication will be recorded on a pregnancy notification form and the subject will be followed up until child birth.

A Suspected Unexpected Serious Adverse Reaction (SUSAR) is an adverse reaction that is both serious and unexpected.

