### **11.6 Sponsor and Chief Investigator Responsibilities**

The Sponsor (or delegate – STU) is responsible for ensuring all SAEs, SARs and SUSARs (except those specified in this protocol as not requiring reporting) will be reported in the appropriate timescale to the MHRA, REC, MPA and the Regional Ethical Review Board (RERB) in Linköping.

STU is responsible for ensuring all SUSARs from Cardiff and Linköping (except those specified in this protocol as not requiring reporting) will be reported in the appropriate timescale to the MHRA, REC, MPA and RERB.

Once an SAE is received by STU, the SAE will be sent to the CI (or appropriate delegate) for clinical review (assessment of causality and expectedness). Fatal and life threatening SAEs should be assessed by the CI within 24 hours of receipt. Non-fatal or non-life-threatening SAEs should be assessed by the CI within 4 days of receipt.

Only SUSARs should be expedited to MHRA, MPA, RERB and REC. STU (UK) and Karolinska Trial Alliance (Sweden) will report according to the following timelines:

Fatal and life threatening SUSARs not later than 7 days after receipt; Non-fatal or non-life-threatening SUSARs not later than 15 days after receipt. Follow up information should be reported within 8 days of receipt of the follow up information. A copy of the SUSAR report should be provided to the Sponsor.

In addition to reporting to the relevant REC, RERB, MHRA and MPA, SUSARs will also be reported to all members of the TMG. The CI shall ensure that all co-investigators receive regular safety updates of SAE's and SUSARs that occur in relation to the IMP in the trial.

Dose interrupting and suspension of dosing will be managed as per the risk mitigation, see section 7.

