#### ***The CI is responsible for assessing expectedness***

No events other than those listed in section 10.2 are expected.

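### A serious systemic hypersensitivity reaction is most naturally read as expected, so it would not trigger the only automatic suspension of dosing in all subjects

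*Protocol*

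**What the plan says.** Protocol section 7 works at two levels.

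- **One subject.** Injections stop in a subject who meets any of three conditions. The relevant one is: "Experiences a serious adverse reaction or an allergic event suggestive of systemic hypersensitivity requiring more than local therapy". The others are a worsening local wheal or flare above 5 cm, and pregnancy.
- **All subjects.** There is a single trigger: "If any individual in the study experiences a SUSAR further dosing of all subjects at all sites will be suspended pending review". The review is by the DSMB, with discussion between the Chief Investigator (CI) and the Sponsor. To restart: "A substantial amendment application will be submitted to the Regulatory Agencies to resume the trial".

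SAP 2.2.2 repeats both levels.

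Whether the all-subject trigger applies depends on definitions elsewhere in the protocol. Section 11.1: "A Suspected Unexpected Serious Adverse Reaction (SUSAR) is an adverse reaction that is both serious and unexpected". Section 11.6 gives the expectedness decision to the CI and adds: "No events other than those listed in section 10.2 are expected". Section 10.2, on hypersensitivity, says: "Systemic hypersensitivity may manifest as shortness of breath; skin rash; tissue swelling; collapse". On reporting, 11.6 says: "Only SUSARs should be expedited to MHRA, MPA, RERB and REC". It refers any suspension of dosing back to section 7.

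**The concern.** This is a first-in-man study, and its primary objective (4.1) names induction of hypersensitivity. Section 7 describes "the only anticipated severe reactions is one of hypersensitivity which, if systemic, would be apparent within 60 mins of intradermal dosing". The automatic halt clearly covers a serious reaction that nobody foresaw. On the most natural reading, it does not cover the one severe reaction that the protocol does foresee.

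Listing an event so that staff watch for it is different from having human experience that makes a serious case expected. The documents report no such experience: according to section 3.2, earlier studies gave the peptide without gold, with no evidence of toxicity beyond transient local redness.

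If the text is followed as written, other subjects could be injected after a serious product-related systemic reaction and before the DSMB has considered it, unless somebody decides to intervene.

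**Working it through.** The plan has no figure to reproduce. The 8 subjects are a judgement (section 14), and no operating characteristic is given for the stopping rule. The check is mainly one of text.

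**Step 1. A worked case.** A subject collapses after an injection, receives adrenaline and is admitted.

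1. Serious? Yes: inpatient admission is enough under 11.1.
2. A reaction? Yes, if the Principal Investigator (PI) judges it related (11.4).
3. Does that subject stop? Yes, under the second individual condition in section 7.
4. Unexpected? The guide in 11.6 is section 10.2, which names collapse and gives no grade. The table of contents numbers this section 10.3, but the body heading is 10.2 and section 7 also cites 10.2, so the reference is clear.
5. A SUSAR? On that reading, no.
6. Consequence: the event is still reported under 11.6 but not expedited, and section 7 does not suspend the other subjects.

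**Step 2. Does another provision hold the other subjects' injections?**

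| Provision | Automatic hold for others after such a reaction? |
|---|---|
| Sharing of serious events between sites within 24 hours, and weekly calls (section 7) | No, information only |
| Sentinel lock-out (section 7) | No. It is a fixed 24 hours after the first subject's first dose |
| Condition that no serious events are observed (6.8, 7, 10.2) | No. It governs observation times; no action is stated if one occurs |
| Observation and resuscitation cover (10.2) | No, but it limits harm |
| DSMB meeting on concern (11.3) | No, judgement |
| Urgent safety measures (11.7) | No, judgement |
| DSMB responsibility to suspend (21.3) | No, judgement |
| Withdrawal criterion (8.2) | No, affected subject only |
| DSMB reports after the sentinel and 4th patients' first injections (SAP 5.3.2) | No. Scheduled, but no pause attached |

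**Step 3. Illustration of size.** The documents give no reaction rate, so the per-patient risk p is assumed, equal and independent across 8 subjects who are all dosed.

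- At least one case: A = 1 − (1 − p)^8
- At least two cases: B = A − 8p(1 − p)^7
- A further case, given at least one: B / A

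| p | A | B | B / A |
|---|---|---|---|
| 1% | 0.0773 | 0.0027 | 3.5% |
| 5% | 0.3366 | 0.0572 | 17.0% |
| 10% | 0.5695 | 0.1869 | 32.8% |
| 20% | 0.8322 | 0.4967 | 59.7% |

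For example, at p = 5%: A = 1 − 0.95^8 = 0.3366, and B / A = 0.0572 / 0.3366 = 0.170.

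**Step 4. A separate point on timing.** Even where a reaction would prove to be a SUSAR, the halt can wait for the CI's expectedness review. Under 11.6 this is due within 24 hours of receipt for a fatal or life-threatening event and within 4 days otherwise. It follows the PI's report, which is due immediately and within 24 hours (11.4).

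**The case against.** The strongest reply is that the text does not settle expectedness. The sentence in 11.6 excludes events outside 10.2; it does not say that every degree of a listed event is expected. It stands under a heading that gives the decision to the CI. The list in 10.2 is bedside guidance on what to look for. Section 11.1 does not define unexpected, and section 11 takes its definitions from regulations that are not reproduced. A CI could therefore call a collapse needing adrenaline unexpected, and the halt would follow. This stands: the documents do not establish that such a reaction could never be a SUSAR. But the only written reference names collapse without a severity limit, so a mandatory halt rests on the CI departing from the plain reading.

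The second reply is that the safeguards in Step 2 are substantial and would probably be used. That also stands. A reader might infer that dosing would simply carry on unchecked; the documents do not support that. What they lack is a hold that needs no decision.

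Two stronger numerical readings should also be resisted.

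- A reader might take the chance of a further case among the 7 others as 1 − (1 − p)^7, which is 7%, 30%, 52% and 79% at the same assumed risks. That applies only if the first-dosed subject reacts before the others are exposed.
- A reader might add 24 hours and 4 days and claim a 5-day delay in the collapse example. Such an event would most naturally be life-threatening, so the CI's limit is 24 hours. If the event is classed as expected, no wait for SUSAR status arises at all.

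**Conclusion.** The point holds as a gap in the mandatory rule. On the most natural reading, a serious systemic hypersensitivity reaction stops the affected subject but triggers neither the all-subject suspension nor expedited reporting. No other provision automatically holds the remaining injections. This rests on the text alone and not on any assumed rate.

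The percentages in Step 3 are illustrative. They use assumed risks and suppose that nobody intervenes, so they do not measure what an automatic pause would prevent.

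The discretionary safeguards keep this from being a fundamental flaw. It should still be corrected, because it concerns the only severe reaction the protocol anticipates and the correction is short.

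**What to change.** 1. In 11.6, state that no serious adverse reaction is expected, and that only the non-serious local reactions described in 10.2 are. A serious hypersensitivity reaction is then a SUSAR and is expedited. This alone closes the gap in expectedness.
2. In section 7 and SAP 2.2.2, make the all-subject trigger a SUSAR or any serious adverse reaction, whether or not expected. It should act on the PI's assessment of seriousness and causality, with no further injections until DSMB review. This also removes the wait described in Step 4.

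**Cost.** The drafting is a few sentences. If the trigger is met, all dosing pauses, and under section 7 a substantial amendment is needed to resume. Under 5.4 a dose counts as missed once the interval exceeds 42 days. A subject due on the day of the halt, 28 days after the last dose, therefore has 42 − 28 = 14 days in hand; one dosed that day has 42. A longer pause means missed doses and additional subjects, so that 8 receive all three doses. On the assumed risks of 1%, 5%, 10% and 20%, the chance of at least one such pause among 8 subjects is column A: 8%, 34%, 57% and 83%. The pause arises only when a serious product-related reaction has occurred, which is when review before further injections is warranted.

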## **8 WITHDRAWAL/EXIT CRITERIA**

### **8.1 At any time**

- Patient withdrawal of consent

### **8.2 After receipt of first dose**

- Potential Serious Adverse Event attributable to the IMP.

### **8.3 Subject becomes pregnant**

- No further doses will be given and the subject will be invited to attend trial follow up visits, to obtain outcome data in accordance with the planned analysis.
- The pregnancy will be recorded on a pregnancy notification form and the subject will be followed up until child birth.

## 8.4 Treatment of Withdrawn Subjects

### 8.4.1 Follow-up of Withdrawn Subjects

Care for withdrawn subjects will return to their referring diabetologist, however they will also be invited to attend trial follow up visits, to obtain outcome data in accordance with the planned analysis.

### 8.4.2 Management of Data from Withdrawn Subjects

All withdrawn patients will be invited to attend follow up visits to provide outcome data for the purposes of the planned analysis.

## 9 END OF STUDY

REC, the MHRA, MPA and the Regional Ethical Review Board in Linköping will be notified of end of study within 60 days of the last visit of the last participant taking part in the trial.

## 10 PHARMACOVIGILANCE

### 10.1 Specification, timing and recording of safety parameters

The major associated safety parameters are evidence of induction of hypersensitivity and exacerbation of  $\beta$ -cell specific autoimmunity with accelerated  $\beta$ -cell loss. To address general safety concerns at screening and 0, 4, 8 and 14 weeks a physical examination will be conducted. A review of AEs will be performed at all visits and blood will be drawn at screening, weeks 4, 9, 14 & 20 to examine the full blood count; urea, electrolytes and creatinine; liver function tests; (prothrombin time, total bilirubin, total protein, albumin, AST (SGOT), SGPT (ALT), alkaline phosphatase; thyroid stimulating hormone; immunoglobulins (G, A, M); calcium; magnesium, phosphate, lipid profile (total cholesterol, LDL, HDL, triglyceride). Urinalysis for pH blood, protein, urine beta-2-microglobulin and albumin/creatinine ratio will be done at screening and visits 1, 2, 4, 5 and 6 and urine for cystatin-c will be collected at visits 1, 4, 5 & 6. A urine pregnancy test will be completed on females only, at all trial visits. At visits 1, 1b, 3b, 4, 5 and 6 blood and urine samples will be taken for gold concentrations to enable assessment of gold excretion. Laboratory measurements for these will be performed at the Midatech Pharma laboratory, Spain.

The safety of the investigational medicinal product (IMP) C19-A3 GNP has been extensively studied in pre-clinical toxicity studies. No signs of toxicity and no significant adverse effects in the organs and the >40 tissues examined were seen, not even at doses that were up to 500-fold higher than the intended dose in this clinical study, and given daily during 14 consecutive days. The studies revealed that the major organ of accumulation and excretion of the gold nanoparticles is the kidney, and to a much lesser extent the liver and spleen. Significant quantities of gold were only detectable in kidneys, which collected on average 30 % of the total dose administered (in rats) over the 14 day period, with a half-life of elimination of circa

17 days. Because the kidney was the most exposed vital organ in the animals used for the pre-clinical safety studies, a number of markers of kidney function will be monitored in the patients. Electrolytes, urea, creatinine, calcium, phosphate, and magnesium levels will be tested in blood. Urinalysis for blood, protein (cystatin-c) and beta-2-microglobulin will be performed in addition. A final analysis will be performed 12 weeks after the last dosing. There will also be an optional analysis at 12 months/ 52 weeks post last dose. For safety reasons, there will be an optional contact hypersensitivity/ skin testing to be performed anytime post final dose.

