**Table 1: Schedule of study visits**

Visit number	Screening		Pre V1	Treatment							Follow up				Optional	
	-2	-1		1	1b	1C	2	3	3b	3C	4	Pre V5	5	6	7	any time post dosing
Weeks	These visits can be combined. Treatment must start within 3 months of screening commencing 		A minimum of 72 hours prior to visit 1	0	1 day post visit1	3 to 5 days post visit 1	4	8	1 day post visit3	3 to 5 days post visit 3	9	A minimum of 72 hours prior to visit 5	14	20	52	
Days				0			28	56			63 (or one week post final injection)		98	140 (85 days post final dose)	366 (311 days post. final dose +/- 14 days)	
Informed consent	X															
Study drug administration				X			X	X								
Follow up telephone call 24 hours post IMP				X			X	X								
Physical Exam & ECG	X			X			X	X					X		X	
 Serum for AABs and immune markers				X							X		X		X	
DRB1*0401 genotype	X															
MMTT				X									X		X	
Photographs at injection site				X			X	X			X		X	X	X	
Blood sample to accompany skin studies (optional)								X								
Stitch removal from biopsy site (optional)										X						
urine or random serum c-peptide post meal		X		X									X		X	
72 hour continuous glucose monitoring			Attach CGM	X								Attach CGM	X		X	
Serum for Cystatin C				X							X		X	X	X	
Urinalysis for blood, protein, and beta-2 microglobulin		X		X			X				X		X	X	X	
Serum and urine (morning) sample to measure gold concentrations				X pre dose	X 				X 		X		X	X	X	
T cell (immune biomarker) assays (blood)				X				-			X		X		X	
 LN aspiration 0/3-5d				X		X		X		X						
 Safety blood samples		X		X			X				X		X	X	X	
HbA1c measurement		X		X			X				X		X		X	
Vital signs	X	X		X			X	X			X		X	X	X	
Adverse Event assessment/con meds		X	X	X	X	X	X	X	X	X	X	X	X	X	X	
Urine pregnancy test		X		X			X	X					X	X		
Record of insulin use	X			X			X	X					X		X	
 Blood glucose profile/insulin usage				X			X	X					X	X	X	

Assessment of glycaemic control/review blood sugar recordings				X				X	X					X		X	
Skin biopsy (optional) 																	X
Contact hypersensitivity testing (optional) 																	X
Suction blister (optional) 																	X
XHFS survey				X										X			
ADDQoL				X										X		X	
DTSQs				X										X		X	
DTSQc														X			

Screening can be up to 3 months

Treatment visits 1, 2 and 3 should be every 28 days +/- 3 days and follow up visit 5 should be at 14 weeks +/- 1 week

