**Figure 3 Blood draw schedule:**

	Screening		Treatment					Follow-up				
Visit no:	-2	-1	1	1b	2	3	3b	4	5	6	7	post
Weeks			0		4	8		9	14	20	52	final
Days			0	1	28	56	57	63	98	140	366	dose
Safety blood samples HbA1c & glucose		11			11			11	11	11	11	
DRB1*0401 and A*02	2											
Serum for Aabs	2											
Serum for insulin cell free DNA	8											
Serum for: Aabs, cystatin-c, insulin cell free DNA, other			10					10	10	10	10	
MMTT			25						25			
Blood to accompany skin biopsies												20
Serum for gold concentrations (morning urine also to be sent)			1	1			1	1	1	1	1	
PBMC's T reg assay, T cells, CD4 & CD8 tetramers, Elispots & biobank storage.			64					64	64*		64	
Flow cytometry			2					2	2		2	
Serum for gold concentration before contact hypersensitivity testing												1
Total	12	11	102	1	11	20	1	88	113	22	113	1

\*in subjects with immune responses of interest visit 4, an additional blood sample up to 70mls (35mls for under 18s) may be requested between visit 4 and visit 6.

Volumes for the study within an 8-week period coincide with guidelines of the National Institute of Health (ie blood collection should be <550ml per 8-week period for adults, and no more than 5ml/kg in a single day and no more than 9.5ml/kg in any 8 week period for under 18's) and are those used by the Type 1 diabetes clinical trial consortium, Type 1 Diabetes Trial Net ([www.diabetestrialnet.org](http://www.diabetestrialnet.org)).

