The procedures are as follows. Start IV line. Obtain baseline blood samples at 0 minutes, and any other test samples required at that visit (e.g. HbA1c, T cell studies, PBMCs islet cell autoantibodies). For each time point blood samples are 1.2 ml fluoride tube for glucose and 1.2 ml serum tube for C-peptide. In addition, for each test the first sample (0 minutes) and the last sample (120 minute for MMTT) will be used to obtain a meter ketone reading, which is recorded. A first blood sample is drawn immediately before the participant starts drinking the liquid meal (formal "baseline samples"). The patient is given the standardized liquid meal: Ensure Plus 6 ml/kg (Maximum 360ml) to be ingested within 5 minutes. Blood samples are drawn at times: 15, 30, 60, 90 and 120 minutes, after the end of ingestion of Ensure Plus (note: time runs from the start of ingestion). After the test is completed, the participant eats and receives insulin as appropriate and prescribed by the local investigator. A urine sample at the 120 minute time point will also be collected for c-peptide creatinine ratio as an alternative marker of insulin production.

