5.3.3 Gold concentration

At visits 1, 1b, 3b, 4, 5 and 6 blood and urine samples will be taken for gold concentrations to enable assessment of gold excretion. Laboratory measurements for these will be performed at the LGC laboratory, Cambridgeshire. Concentration of gold for each patient over time will be analysed by half-life of elimination at the end of the study.

The major organ of accumulation and excretion of the gold nanoparticles is the kidney. Safety reports on markers of kidney function in blood (levels of electrolytes, urea, creatinine, calcium, phosphate, and magnesium) and urine (blood in urine, protein in urine, cystatin-c and beta-2-microglobulin) have already been covered in 5.3.1 and 5.3.2.

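### Urinary gold is planned as an uncorrected concentration in an untimed morning sample, the half-life has no stated matrix, and the two documents name different gold laboratories

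*Protocol*

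**What the plan says.** **Sampling.** Protocol 10.1 states that, at visits 1, 1b, 3b, 4, 5 and 6, "blood and urine samples will be taken for gold concentrations to enable assessment of gold excretion". Protocol Table 1 describes the collection as "Serum and urine (morning) sample to measure gold concentrations", and the blood draw schedule (Protocol Figure 3) lists 1 ml of serum at each of these visits and at optional visit 7, with morning urine sent alongside. No timed collection, urine volume, creatinine ratio or specific-gravity correction is described for gold.

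**Analysis.** SAP 5.3.3 states: "Concentration of gold for each patient over time will be analysed by half-life of elimination". It does not give the matrix, the model or the visits to be fitted.

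**Other urine measures.** C-peptide is expressed against creatinine; Protocol 6.18.1 states: "A urine sample at the 120 minute time point will also be collected for c-peptide creatinine ratio". Albumin is expressed as the albumin/creatinine ratio (ACR), which Protocol 10.1 schedules at screening and visits 1, 2, 4, 5 and 6.

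**Laboratory.** Straight after the gold sampling sentence, Protocol 10.1 states: "Laboratory measurements for these will be performed at the Midatech Pharma laboratory, Spain". In the matching place, SAP 5.3.3 says the measurements will be "performed at the LGC laboratory, Cambridgeshire".

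**The concern.** The concentration of a substance in a single urine sample is its excretion rate divided by urine flow. It therefore changes with how dilute the urine is, even when excretion does not. In people with diabetes, glucose-driven urine volume is a plausible further source of variation, and the trial admits HbA1c up to 10%.

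Protocol 10.1 names the kidney as the main organ of accumulation and excretion in the preclinical work. Serum shows circulating gold, and urine is the direct human evidence on renal excretion. If urinary gold is read uncorrected, a dilute sample soon after a dose can look like retention, and a dilute late sample can look like fast clearance.

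Creatinine at visits 1b and 3b may not be obtainable later unless it is planned, because no urine creatinine is scheduled there. Two named laboratories for one assay also leave it unclear where the samples go.

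**Working it through.** The plan gives no precision, power or variability figure for gold, so there is nothing of its own to reproduce. The following is an illustration.

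**Inputs**
- Visit days from Protocol Table 1: dose 3 on day 56, visit 4 on day 63, visit 5 on day 98, visit 6 on day 140. Visit 3b is day 57 (Protocol Figure 3). Times after dose 3 are 1, 7, 42 and 84 days.
- True half-life: 17 days, the rat figure in Protocol 10.1. The documents give no human value.
- Dilution CV between visits: 30%, 50% or 80%. These are assumptions.
- Ignored: carry-over from doses 1 and 2, assay error and values below the detection limit.

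**Expected fall, visit 3b to visit 4.** Over 6 days the ratio is 2^(−6/17) = 0.78, a 22% fall. A dilution change of 2^(6/17) = 1.28-fold hides it. On those two samples alone, simulation gives a flat or rising slope in 28% of patients at CV 30% and 36% at CV 50%.

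**Expected fall, visit 3b to visit 6.** Over 83 days it is 2^(83/17) = 29.5-fold. A 2-fold dilution difference between these two samples gives an apparent half-life of 83/(83/17 + 1) = 14.1 days or 83/(83/17 − 1) = 21.4 days. The decline is not reversed.

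**One patient, four visits, log-linear fit**
- k = ln 2/17 = 0.0408 per day.
- Mean time is 33.5 days. Sxx = 32.5² + 26.5² + 8.5² + 50.5² = 4381, and √4381 = 66.2.
- Log-scale SD: s = √ln(1 + CV²). SE of slope = s/66.2. The 95% limits for the half-life are ln 2/(k ± 1.96 × SE).

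| Dilution CV | s | SE | 95% range (days) |
|---|---|---|---|
| 30% | 0.294 | 0.0044 | 14.0–21.6 |
| 50% | 0.472 | 0.0071 | 12.7–25.9 |
| 80% | 0.703 | 0.0106 | 11.3–34.8 |

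A simulation of 200,000 patients agreed to within 0.1 day, with the median at 17 days throughout.

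**Single values.** The 95% uncertainty of one urine concentration is exp(1.96 × s): 1.8-fold, 2.5-fold and 4.0-fold either way at the three CVs.

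**Possible gain.** If creatinine correction cut the CV from 50% to 10% (assumed), s would be 0.100 and the range 15.9–18.3 days.

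**Where creatinine is already implied.** The gold visits are 1, 1b, 3b, 4, 5 and 6, and the ACR visits are 1, 2, 4, 5 and 6. They overlap at 1, 4, 5 and 6, and not at 1b or 3b. The documents do not say that the ACR and gold come from the same void.

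**The case against.** The strongest reply is that serum is paired with urine at every gold visit and the SAP names no matrix. A reader might infer that excretion is to be judged from urine alone, so that dilution decides the result. The documents do not support that, because a serum half-life would be unaffected.

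Random dilution also adds imprecision rather than bias. With the slope pooled over 8 patients, the range at CV 50% is 15.2–19.3 days. A larger swing appears if only visits 3b and 5 are compared: over 41 days, a 2-fold dilution difference gives 41/(41/17 + 1) = 12.0 or 41/(41/17 − 1) = 29.0 days. That comparison leaves out visit 6, which is planned.

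A reader might also infer that gold is the only urine analyte left uncorrected. It is not: Protocol 10.1 states no ratio for urine beta-2-microglobulin or cystatin-C either. Nor do the documents say why C-peptide and albumin are expressed as ratios.

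Further, Protocol 6.7 promises a laboratory manual and the SAP refers to a Data Transferral Plan, either of which may cover creatinine. Gold is not a listed endpoint or stopping criterion, and renal safety has other markers.

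These replies limit the point to urine-based results and lower its priority. They do not supply a dilution correction, a matrix for the half-life, or creatinine at visits 1b and 3b.

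**Conclusion.** The point holds for urine. As written, the plan allows a per-patient half-life to be fitted to uncorrected concentrations in untimed morning urine, and it does not say whether serum or urine is meant. Under the stated assumptions, the cost is a single-patient 95% range of about 14–22 days (CV 30%) to 11–35 days (CV 80%) around a true 17 days, and short-interval comparisons such as visit 3b to visit 4 that tell little.

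These sizes rest on a rat half-life and assumed dilution CVs. A longer human half-life would make dilution matter more, but the documents give none.

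The laboratory conflict is a separate, plain contradiction between the documents. A reader might infer that one patient's series will be split between two assays. Each document names a single laboratory, so nothing shows that a split is planned.

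Because gold is analysed descriptively, this is a minor but cheap improvement.

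**What to change.** - **Protocol 10.1:** measure creatinine in every urine aliquot sent for gold, at visits 1, 1b, 3b, 4, 5 and 6 and at visit 7 where attended.
- **SAP 5.3.3:** report and analyse urinary gold per mmol creatinine, report serum gold separately, and state which matrix, model and visits give the half-life.
- **Both documents:** reconcile the named laboratory, or explain the change, and assay each patient's full series in one laboratory.

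The cost is 6 or 7 routine creatinine assays per patient on urine already collected, or 48 to 56 for 8 patients, plus a few lines of text. The limitation is that creatinine output itself varies, so the correction reduces the dilution error without removing it.
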